#### Design and Outcomes

Using a pragmatic trial design, *this project will embed and test the feasibility of a novel best practice-based approach*, MIND at Home, within PC to enhance and elevate the role of existing PC staff to Memory Care Coordinators (MCCs), increase PC access to interdisciplinary collaborative care, and systematically combines the benefits of clinic-based services with home- or telephone/video-based assessment to support family-centered care planning and implementation for PLWD and their care partners. Weekly virtual collaborative learning sessions that include geriatric psychiatry consultants augment the PC care team's work to support the development and mastery of, and confidence in, dementia assessment and care management skills at the PC sites. Our *overarching goal* is to test and establish feasibility, acceptability, fidelity, and sample size/referral rate data for MIND at Home in PC to prepare for a future multi-site embedded pragmatic trial.

- Aim 1: Evaluate the feasibility and validity of eligible PLWD identification, referral, and enrollment in a best practice-based dementia care coordination program (MIND at Home) at 3 primary care clinics.
- Aim 2: Evaluate the feasibility, acceptability, and fidelity of implementing MIND at Home in 3 primary care clinics in 2 geographically and demographically diverse integrated health systems.
- Aim 3: Evaluate the feasibility of ascertainment of patient-level outcomes over time using electronic health record (EHR) data.

Embedding a collaborative, best-practice based approach such as MIND at Home into PC is a potentially powerful strategy to organize care, improve quality, reduce costs, and maximize population-level benefit for PLWD. This proposal tests the feasibility of implementing MIND at Home into PC in a racially, ethnically, and geographically diverse PLWD population to prepare for a multisite ePCT to evaluate effectiveness, and eventually to support broader dissemination and uptake in PC.

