### **3 STUDY DESIGN**

#### **3.1 Overview of study design and procedures**

Using a pragmatic trial design, 150 community-residing PC PLWD will be enrolled and receive MIND coordination services for 3 months to test program recruitment and implementation feasibility in PC practice settings. (An additional 100 patients will serve as a data validation arm to demonstrate the feasibility of collecting and validating data from large health systems and will not be enrolled in the intervention.) Enrollees will be recruited through EHR diagnosis and PC referrals. They will undergo a program intake screen (in-clinic or by phone) with a member of the PC team or the memory care coordinator (MCC) to establish program interest and identify the care partner. Interested and eligible enrollees will receive an office- plus home- or telephone/video-based dementia care assessment by the MCC with input from the PC care team. Assessment will be followed by collaborative family-centered care planning, and care plan implementation by an interdisciplinary PC-based team, supported by regular cased-based learning sessions. The primary (hospital transfers, i.e., admissions, ED visits, observation stays) and secondary outcomes (polypharmacy, antipsychotics, acetylcholinesterase, and memantine) will be obtained from regularly collected EHR data.

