#### **4.1 Inclusion Criteria**

Participants must meet all the inclusion criteria to participate in this study:

- Community residing adults,  $\geq 18$  years
- PLWD defined in one of two ways:
  - A diagnosis using algorithms based on CMS' Chronic Care Warehouse definition of Alzheimer's Disease, Related Dementias, Related Disorders, and Senile Dementia. This definition includes those who have an eligible ICD-9/ICD-10, CPT4, or HCPCS code on any eligible claim (i.e., inpatient, outpatient, SNF, or home health visit or stay) in the past three years or a diagnosis on the patient problem list; OR
  - A dementia medication including donepezil, donepezil/memantine combination, galantamine, rivastigmine, aducanumab, or memantine on the patient medication list or a pharmacy claim in the past three years.
- Actively receiving primary care services at one of three primary care practices within two participating health care organizations selected as study sites.
- Have a reliable care partner who speaks English (or a language spoken by the Memory Care Coordinator).
- Willing to participate in all study home or telephone/video visits and related activities for the entire length of the study (3 months).

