#### **4.3 Study Enrollment Procedures**

PLWD will be identified in the EHR of their respective HCOs and approached in two ways. PLWD who present with their care partners for an outpatient office visit will be invited to participate in the program and provided a program information sheet (see Appendix C). After establishing eligibility, dyads can choose to enroll by scheduling an initial home or telephone/video visit with the MCC. Enrollment will begin with an initial needs assessment (the JHDCNA, Appendix B) during a home or telephone/video visit. Telephone intake will be supplemented with a home visit at a later date or photos of the living situation to identify safety issues or ways to improve the PLWD's care. Sites will also identify PLWD in the EHR who meet program eligibility criteria but are not scheduled for a visit. To ensure equity, racial minorities and other underserved populations will be prioritized and approached using culturally sensitive processes to ensure a representative sample of participants. Care partners/PLWD will be contacted by telephone to enroll in the program using a script, based on local context and cultural adaptation of an existing script (see Appendix D). Recruitment will be supported with existing MIND outreach and engagement resources. To assess feasibility and validity of eligible patient identification, referral, and enrollment, MCCs will electronically record the number of patients flagged as eligible, referred, enrolled, and retained or who refused, were unreachable, or lost to follow-up. Referral, recruitment, patient acceptance, and attrition rates will be calculated to assess the feasibility of use of the algorithm and of the

recruitment protocol. MCCs will enroll a minimum of seven PLWD every other week for a maximum caseload of 42, to accommodate other non-dementia patients who may be part of the MCC total caseload.

As this is a minimal risk, best-practice based quality improvement intervention, a waiver of consent will be requested for this study for both the intervention patients and the data validation arm cohort. Further justification is described in section 11.2.

Patients will not be randomized for this pilot study.

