#### Screening by Clinic Staff

PLWD will be identified in the EHR of their respective HCOs, by clinic staff, as ever having a diagnosis of ADRD or prescription for a dementia-related medication, on an administrative claim, patient problem list (Dx), or patient medication list (Rx) for the duration of time the patient has data in the EHR. Patients with an existing diagnosis of mild cognitive impairment may be assessed for ADRD during the visit by their provider. Patients must be living at home and in the care of an informal care partner. Patients eligible for the study based on EHR data will be flagged prior to their visit. Once the provider has confirmed eligibility by confirming diagnosis or medication and living situation, eligible PLWDs and their care partners will be invited to participate in the program. For PLWD without a scheduled visit, care partners/PLWD will be contacted by telephone to enroll in the program using a script, based on local context and cultural adaptation of an existing script. (See Appendix D.)

After establishing eligibility, enrollment will be initiated by scheduling an initial home, telephone, or video visit with the MCC. Enrollment will begin with a needs assessment (JHDCNA) during the intake visit.

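### Aim 1 promises to evaluate the validity of patient identification, but no planned measure can show whether flagged patients have dementia, and the provider check lets a medication-only flag pass on the fact that raised it.

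*Combined protocol and SAP*

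**What the plan says.** The Précis sets the aim: "Aim 1: Evaluate the feasibility and validity of eligible PLWD identification, referral, and enrollment". Sections 4.3 and 10.1 repeat the pairing of feasibility and validity, and Section 10.2 lists validity of patient identification among the data that Memory Care Coordinators (MCCs) collect.

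The means of assessment is in Section 4.3: "To assess feasibility and validity of eligible patient identification, referral, and enrollment, MCCs will electronically record the number of patients flagged as eligible". The list continues with numbers referred, enrolled, retained, refused, unreachable and lost. Sections 4.3 and 10.1 derive four rates from these counts (referral, recruitment, acceptance, attrition) and say that the rates assess the feasibility of using the algorithm.

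Section 4.1 has "PLWD defined in one of two ways": a diagnosis found by the claims-based algorithm or on the problem list, or a dementia drug on the medication list or in a pharmacy claim. Section 6.2.1 has clinic staff find patients in the EHR "as ever having a diagnosis of ADRD or prescription for a dementia-related medication, on an administrative claim, patient problem list (Dx), or patient medication list". The provider's step follows: "Once the provider has confirmed eligibility by confirming diagnosis or medication and living situation". For the second contact route the text is: "For PLWD without a scheduled visit, care partners/PLWD will be contacted by telephone to enroll in the program using a script".

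**The concern.** An evaluation of validity needs something to compare the flag with. The plan names no reference standard, no confirmation rate and no predictive value. The provider step is the natural place to obtain one, but it accepts either of the facts that can raise the flag. A patient prescribed a dementia drug without having dementia would be flagged by the drug and could be confirmed by the drug.

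The pilot exists to prepare a full trial, and the identification algorithm is one of the things it is meant to test. Aim 1 could be reported as favourable on referral and enrollment rates alone, however many flagged patients do not have the condition. Any such patients who enroll would also contribute to the fidelity and outcome data.

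**Working it through.** The documents give no figure for identification accuracy (no target, sample or threshold), so there is nothing to reproduce. The check is mainly a comparison of texts.

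**1. Flag against confirmation (Sections 4.1 and 6.2.1)**

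| Flag raised by | Confirmed by | New information on dementia |
|---|---|---|
| Diagnosis code or problem-list entry | Diagnosis, or medication | Possible, if confirming a diagnosis means fresh judgement; no criteria given |
| Dementia drug only | Diagnosis, or medication | None needed; the drug satisfies both |
| Either, no scheduled visit | No provider step stated | None stated |

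Living situation is also confirmed, but it does not bear on dementia status.

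**2. Other places where a dementia check might be found**

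- *Intake screen (Section 3.1).* Held "with a member of the PC team or the memory care coordinator (MCC) to establish program interest and identify the care partner". It is not described as diagnostic.
- *Chart review (Section 10.1).* It stands in the Aim 3 paragraph, directly after the primary and secondary outcomes, and is not tied to dementia status.
- *The 100-patient validation arm (Section 11.2.1.3).* Its purpose is feasibility of extraction and data quality.
- *Provider assessment for dementia (Section 6.2.1).* Optional, and mentioned only for patients with recorded mild cognitive impairment.
- *Baseline assessment (Section 6.2.2).* None beyond demographics. The JHDCNA in Section 5.1 assesses care needs.

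None supplies a recorded judgement of dementia that can be set against the flag.

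**3. What a record re-read would show on the medication-only branch (illustration; all inputs assumed)**

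Let P be the true share of flagged patients with dementia and c the share of false flags that the check re-confirms, with all true flags confirmed. Apparent confirmation rate = P + (1 − P) × c.

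- c = 1: the rate is 100% at P = 60%, 70%, 80% or 90%.
- c = 0.95: at P = 60%, 0.60 + 0.40 × 0.95 = 98.0%; at P = 90%, 0.90 + 0.10 × 0.95 = 99.5%.

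A check that only re-reads the record therefore barely separates a good rule from a poor one.

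**4. Possible number affected (assumed ranges)**

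Enrolled = 150 (Précis, Section 9.5). Assume that 10-30% enter by medication only, which is 15 to 45 patients, and that 10-30% of those lack dementia.

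- Low: 150 × 0.10 × 0.10 = 1.5 patients, 1%.
- High: 150 × 0.30 × 0.30 = 13.5 patients, 9%.

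**5. Precision if the judgement were recorded**

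95% Wilson interval: [p + z²/2n ± z√(p(1−p)/n + z²/4n²)] / (1 + z²/n), with z = 1.96 and an assumed p = 80%.

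| Patients judged | 95% interval |
|---|---|
| 15 | 54.8-93.0% |
| 45 | 66.2-89.1% |
| 50 | 67.0-88.8% |
| 100 | 71.1-86.7% |
| 150 | 72.9-85.6% |

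The overall figure would be usable for planning. A medication-only figure based on 15 to 45 patients would be rough.

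**The case against.** The strongest reply is that the provider step is an eligibility gate, not the declared validity measure, and that a gate which applies the inclusion criteria is doing its job. This stands. The fault lies in Aim 1, which has no accuracy measure; the gate matters because it is the existing step best placed to supply one.

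A second reply is that the aim concerns eligible patients, and Section 4.1 deliberately defines dementia by the record, so a drug-only patient is eligible by definition. That is fair for a pragmatic trial. But if eligibility is wholly a matter of record, validity adds nothing that the counts test, and the word should be defined or dropped.

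Three stronger readings are tempting, and the documents do not support them:

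- *The whole check is circular.* A reader might infer this, but confirming a diagnosis at a visit can involve clinical judgement, and a provider might find a listed drug outdated. Circularity is clear only for the medication-only branch. A 100% confirmation rate follows there only if the check merely re-reads the record.
- *The telephone route is circular too.* As written it is unchecked. Section 6.2.1 refers to eligibility being established without saying by whom or how, and the telephone script (Appendix D) is not in the text supplied for review. Section 5.1 brings the primary care provider into care planning and has new cases reviewed with dementia specialists, but neither is recorded as validation.
- *Between 1% and 9% of enrolled patients are misidentified.* Both inputs are assumptions, and nothing in the documents points to them. Section 9.1 states no statistical hypothesis and Section 9.5 plans only exploratory analysis, so an effect on outcome results is possible but not shown.

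Finally, a provider who knows the flag, and may have entered the diagnosis or drug, is not an independent assessor. This also stands and limits what the proposed figure can be called.

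**Conclusion.** The point holds in this form. Aim 1 promises an evaluation of validity that the stated counts and rates cannot deliver. The provider step would not fill the gap as written, because medication alone satisfies it, and no provider confirmation is stated for the telephone route. This rests on the text of Sections 4.1, 4.3, 6.2.1, 10.1 and 10.2 and on no numerical assumption. It is more than a missing detail: a team that followed the plan exactly would finish without an answer to half of its first aim.

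The number of patients affected is unknown; about 2 to 14 of 150 is an assumed range. The change is worth making because the pilot is meant to inform a larger trial and the cost is small.

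**What to change.** 1. At the existing provider confirmation step, record one further item: dementia in my clinical judgement, yes / no / uncertain. Keep it separate from whether the code or drug is present. It is a recorded measurement and does not change who is eligible.
2. Report the proportion judged yes, with a 95% confidence interval, by flag route (diagnosis, medication only, both) as the Aim 1 validity result. Keep uncertain answers in the denominator and show their number.
3. Call the result a provider-judged positive predictive value that is not blinded to the flag. State that it says nothing about sensitivity; Section 11.2 itself notes that dementia is under-detected.
4. For telephone-route patients, record the same item when the primary care provider joins care planning (Section 5.1). Report them separately, since they will be enrolled patients only.
5. If this is not done, remove validity from Aim 1 and from the matching text in Sections 4.3, 10.1 and 10.2.

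When the flag is written down for this purpose, its look-back should be reconciled: Section 6.2.1 uses any record in the EHR, while Section 4.1 limits claims to three years.

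The cost is a little provider time per patient judged, including patients who are seen but do not enroll, and a figure that may be less favourable than the flow rates. Blinded adjudication of charts would be a stronger reference but a larger burden, and Section 11.2 describes staffing as minimal.

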### 6.2.2 Enrollment, Baseline, and/or Randomization

#### Enrollment

PLWD and their care partners will be enrolled by the Memory Care Coordinator who will record baseline demographic data of the PLWD available in the EHR, i.e., sex, age, race, ethnicity, and will schedule their initial home, telephone, or video visit. Data will be recorded on a case report form, separate from the EHR. See Appendix B. In addition to baseline demographic data, enrollment date, name of PLWD and care partner, care partner contact information will be collected and recorded.

#### Baseline Assessments

There are no planned baseline assessments aside from the collection of the demographic data listed above for the pilot study.

#### Randomization

Patients will not be randomized for this pilot study.

### 6.2.3 Follow-up Visits

Enrollees will have a minimum of three contacts with the MCC over three months (e.g., mix of phone and in-home visits). Contact intensity will be driven by individual needs and preferences.

There are no required office visits during the intervention.

#### 6.2.4 Completion/Final Evaluation

At the final home, telephone, or video visit during Study Month 3, the MCC will complete a final evaluation of the participant including an assessment of adherence to the care plan.

#### 6.2.5 Program Satisfaction Surveys

##### 6.2.5.1 *Clinic Staff Surveys*

After program completion, brief surveys developed in prior MIND studies will be sent (email or mail) to PC clinic staff to assess experience (satisfaction, perceived benefit, challenges, ways to improve program). The surveys will be used to assess the program and are voluntary. The surveys are included in the request for waiver of informed consent for the clinic staff. We will be surveying clinic staff on program satisfaction as part of the intervention, to solicit feedback and make improvements. We will take their responses into account when measuring feasibility of implementing the intervention into primary care.

The surveys will be anonymous. They will not include the name or identifier of the person taking the survey. They will capture who is being assessed, or the participant for the clinic staff surveys. The surveys will therefore “stand alone” and will not be linkable to the EHR clinical data. The surveys are a regular quality part of the MIND program. We will use the results to inform Aim 2, feasibility of implementing this program into primary care.

##### 6.2.5.2 *Participant Surveys*

After program completion, brief surveys developed in prior MIND studies will be sent (email or mail) to participants/care partners to assess experience (satisfaction, perceived benefit, challenges, ways to improve program). Participant Surveys are included in the Appendix. The surveys will be used to assess the program and are voluntary. The surveys are included in the request for waiver of informed consent for the study participants. We will be surveying them on program satisfaction as part of the intervention, to solicit feedback and make improvements. We will take their responses into account when measuring feasibility of implementing the intervention into primary care.

The surveys will be anonymous. They will not include the name or identifier of the person taking the survey. They will capture who is being assessed, the MCC for the participant surveys. The surveys will therefore “stand alone” and will not be linkable to the EHR clinical data. The surveys are a regular quality part of the MIND program. We will use the results to inform Aim 2, feasibility of implementing this program into primary care.

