## 8 **INTERVENTION DISCONTINUATION**

The intervention may be voluntarily discontinued by a subject at any time. In addition, if a subject is permanently transferred from their home to a long-term care facility, they will no longer be eligible to continue the study. There are no other reasons to discontinue a subject from the intervention as long as they continue to live at home, have an informal care partner, and are willing to participate.

We will continue to collect data on subjects who withdraw voluntarily from participation in the study. All data collection is passive, pulled from the EHR where the subject receives their regular primary care.

Subjects who discontinue before the study has completed will be replaced, if possible, as long as this does not extend the length of the study.

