**Program implementation feasibility (Aim 2).** Implementation feasibility will be assessed by collecting a standard set of process measures and fidelity metrics. For all participant dyads, process measures will be collected by the MCC and submitted monthly to the AMGA research analyst including number, duration, type, and general content of encounters per dyad will be calculated to assess the feasibility of implementation. All process measures will be monitored and stratified by minority participants (rurality, race/ethnicity) to assess differential rates of adherence, attrition/retention. Fidelity will be assessed by tracking completion of core intervention components (# needs assessment completed, # care plans completed, # completed 3 months, # with MCC encounter at least every 3 months), and attendance at weekly virtual learning sessions by team member types (>50% of sessions). Collection of this information is facilitated by documents created for MIND on program implementation fidelity. (See [Appendix A](#).) Fidelity measures will be captured and monitored using a work process template/spreadsheet completed by MCCs for each assigned dyad for each encounter. The template serves as an operations checklist the MCC completes at each home visit/contact that includes each component of the home, telephone, or video visit, the care plan with needs being addressed, actions taken, and follow up plans. All data collected on participants will be collected electronically, encrypted during upload, download, and transfer, using password-protected files, and saved on password-protected computers.

A de-identified version of the management template will be shared with the co-investigators (Drs. [name] & [name]) biweekly (i.e., every other week) for review and feedback. De-identified program implementation data will be sent by the study site to the AMGA research analyst monthly. Acceptability will be assessed from multiple stakeholder perspectives. In the final 2 months of the pilot, brief surveys developed in prior MIND studies will be sent (email or mail) to dyads (post program) to assess experience (satisfaction, perceived benefit, challenges, ways to improve program). The participant survey is included in the Appendix.

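### The dyad satisfaction survey is timed to the end of the program, so on the natural reading dyads who leave early are not asked and Aim 2 acceptability describes mainly those who stayed

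*Combined protocol and SAP*

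**What the plan says.** Acceptability is part of Aim 2 and of the overarching goal (Précis; Section 1.1). Section 10.1 states: "Acceptability will be assessed from multiple stakeholder perspectives". For dyads, the only instrument described is a brief voluntary satisfaction survey.

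- **Section 6.2.5.2:** "After program completion, brief surveys developed in prior MIND studies will be sent (email or mail) to participants/care partners to assess experience".
- **Section 10.1 (Aim 2):** "In the final 2 months of the pilot, brief surveys developed in prior MIND studies will be sent (email or mail) to dyads (post program".

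Section 8 provides for early exit. "The intervention may be voluntarily discontinued by a subject at any time", and "if a subject is permanently transferred from their home to a long-term care facility, they will no longer be eligible to continue the study". On replacement it says: "Subjects who discontinue before the study has completed will be replaced, if possible", provided the study is not lengthened. On data after exit it says: "We will continue to collect data on subjects who withdraw voluntarily from participation in the study", and then: "All data collection is passive, pulled from the EHR where the subject receives their regular primary care".

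Under Section 6.2.5.2 the survey is anonymous, cannot be linked to the EHR data, and records which memory care coordinator (MCC) is being assessed. Section 9.5 plans descriptive, aggregate reporting. It states no survey denominator, response rate or handling of non-response. Sections 4.3 and 10.1 have the MCCs count dyads who were retained, refused, were unreachable or were lost to follow-up, and attrition rates are calculated from these counts.

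**The concern.** A satisfaction survey sent only to those who reach the end of a program is exposed to survivor bias. Dyads who found the program unhelpful or burdensome are more likely to leave and less likely to be asked. The attrition rate shows how many left. It does not show why, or what they thought.

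Acceptability is one of the quantities the pilot is meant to establish for the planned multi-site trial. If leavers' views are missing, the pilot may report higher acceptability than enrolled dyads as a whole experienced. It would also lose the information most useful for improving retention. Because the survey is anonymous and unlinkable, stayers and leavers can be told apart later only if the form itself records completion status.

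**Working it through.** The plan states no figure that depends on this point, so there is nothing to reproduce. The check has two parts: what the sections imply about who is surveyed, and how much it could matter.

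**Who is surveyed**

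1. Section 6.2.5.2 triggers the survey by program completion. Section 10.1 triggers it by a calendar window, with a note that it comes after the program. Neither says whether a dyad that withdrew, was lost or moved to long-term care receives it.
2. Section 8 is the only place that describes data collection after withdrawal, and it describes EHR extraction. A mailed or emailed questionnaire is not passive EHR data, so Section 8 does not fill the gap.
3. The final evaluation in Section 6.2.4 takes place at the Study Month 3 visit, which a dyad that left earlier would not have. No exit questionnaire or reason-for-leaving item is described.
4. Followed as written, the plan therefore has a defined moment for surveying a dyad that stays and none for a dyad that leaves.

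**How much it could matter**

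Input from the documents: 150 enrolled (Précis; Section 9.5). The documents give no withdrawal rate, satisfaction rate or survey response rate. The values below are assumptions, and every dyad asked is taken to respond.

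Let d be the proportion who leave, S the proportion satisfied among stayers and L the proportion satisfied among leavers.

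- Satisfaction among all enrolled = (1 − d) × S + d × L
- Overstatement if only stayers are surveyed = S − [(1 − d) × S + d × L] = d × (S − L)

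With S = 90% and L from 70% down to 30%:

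| d | Leavers out of 150 | Overstatement, L = 70% | Overstatement, L = 30% |
|---|---|---|---|
| 5% | about 8 | 0.05 × 20 = 1 point | 0.05 × 60 = 3 points |
| 10% | 15 | 0.10 × 20 = 2 points | 0.10 × 60 = 6 points |
| 20% | 30 | 0.20 × 20 = 4 points | 0.20 × 60 = 12 points |
| 30% | 45 | 0.30 × 20 = 6 points | 0.30 × 60 = 18 points |

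With no assumption about L, the all-enrolled figure lies between (1 − d) × S (no leaver satisfied) and (1 − d) × S + d (every leaver satisfied):

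- d = 10%: 0.90 × 0.90 = 81%, up to 81% + 10% = 91%
- d = 20%: 0.80 × 0.90 = 72%, up to 72% + 20% = 92%

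The upper ends exceed 90%, so the direction of the bias is likely but not certain.

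Replacement affects the denominator. If leavers were replaced until 150 dyads had completed, 20% withdrawal would mean 150 / 0.80 = 187.5, or 188 enrolled. A report based on 150 would leave out 38 dyads.

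**The case against.** Several points on the other side stand.

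- **Leavers are not expressly excluded.** A reader might infer that the plan restricts the survey to completers. It does not say so. Section 6.2.5.2 addresses participants and care partners without restriction. Section 6.2.5.1 uses the same timing phrase for clinic staff, who have no individual three-month enrollment, so it could mean the end of the program as a whole. Completers-only is the natural reading and not a stated rule.
- **The two timings need not conflict.** A reader might infer a contradiction between Sections 6.2.5.2 and 10.1. If program completion means the end of the whole program, they agree. What remains is that a reader cannot tell whether the survey is sent per dyad or once near the end.
- **Leaving is not the same as dissatisfaction.** Section 8 permits withdrawal without predicting a rate, and a move to long-term care says nothing about satisfaction.
- **Attrition is reported.** Readers would see it beside the satisfaction results, and staff surveys add a second perspective. Neither gives the views of the dyads who left.
- **The loss may not be irrecoverable.** The survey form (Appendix E) is not in the text available for review, so it may already record completion status.
- **The numbers are illustrative.** The plan sets no acceptability threshold, so no planned decision is shown to change.
- **Coding the form has a privacy cost.** With about 150 / 3 = 50 dyads per clinic and an assumed 10% withdrawal, each clinic would have about five leavers. A clinic code on top of the MCC already captured could make answers recognizable.

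**Conclusion.** The point holds as a design weakness, not as an error. The sections give no route by which a dyad that discontinues is surveyed, and Section 8 confines collection after withdrawal to EHR data. Unless sites choose to do otherwise, Aim 2 acceptability among dyads would describe mainly those who stayed.

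The size is unknown. The figures of 2 to 6 points at 10% withdrawal and 4 to 12 points at 20% rest on assumed satisfaction of 90% in stayers and 30% to 70% in leavers, with full response. They show scale and are not an estimate. The documents do not support saying that acceptability will be overstated by a given amount, or that the plan deliberately omits leavers.

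The consequence is modest, because the pilot is descriptive and the outcome analyses do not use the survey. The change is still worth making, because views not collected when a dyad leaves are hard to obtain later.

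**What to change.** In Sections 6.2.5.2 and 10.1, state in the same words that the survey goes to every enrolled dyad at its own exit from the program, whether by completion or discontinuation, and that this includes dyads who are replaced. In Section 8, add the survey as an exception to passive-only collection after withdrawal.

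Add one non-identifying completed/discontinued item to the form if it lacks one. Do not add a clinic code, since the MCC is already captured.

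In Section 9.5, report the response rate and satisfaction by that status, pooled across clinics, with all enrolled dyads as the denominator. Dyads who cannot be reached count as non-respondents.

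This is a cheap improvement. It costs a few more mailings and a few protocol sentences. Response among those who left will probably be lower, so their results will be imprecise. Contacting people who have withdrawn may need a minor IRB modification; Section 11.2 puts review of consent-protocol modifications at 3 to 4 weeks, so the change is best made before enrollment starts.
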